#### **F1b. Unanticipated Problems (UP)**

The Office for Human Research Protections (OHRP) considers unanticipated problems involving risks to participants or others to include, in general, any incident, experience, or outcome that meets all of the following criteria:

- Unexpected in terms of nature, severity, or frequency given (a) the research procedures that are described in the protocol-related documents, such as the IRB-approved research protocol and informed consent document; and (b) the characteristics of the participant population being studied;
- Related or possibly related to participation in the research (“possibly related” means there is a reasonable possibility that the incident, experience, or outcome may have been caused by the procedures involved in the research); and
- Suggests that the research places participants or others at a greater risk of harm (including physical, psychological, economic, or social harm) than was previously known or recognized.

#### **F1c. Serious Adverse Event (SAE)**

A serious adverse event (SAE) is one that meets one or more of the following criteria:

- Results in death;
- Is life-threatening (places the participant at immediate risk of death from the event as it occurred);
- Results in inpatient hospitalization or prolongation of existing hospitalization;
- Results in a persistent or significant disability or incapacity; or
- Results in a congenital anomaly or birth defect.

An important medical event that may not result in death, be life threatening, or require hospitalization may be considered an SAE when, based upon appropriate medical judgment,

the event may jeopardize the participant and may require medical or surgical intervention to prevent one of the outcomes listed in this definition.

## **F2. Characteristics of an Adverse Event**

### **F2a. Relationship to Study Procedures**

To assess relationship of an event to the study procedures, the following guidelines are used:

1. Related (Possible, Probable, Definite)
  - a. The event is known to occur with the particular study procedure.
  - b. There is a temporal relationship between the study procedure and event onset.
  - c. The event abates when the study procedure is discontinued.
  - d. The event reappears upon re-introduction of the study procedure.
2. Not Related (Unlikely, Not Related)
  - a. There is no temporal relationship between the study procedure and event onset.
  - b. An alternate etiology has been established.

### **F2b. Expectedness of SAEs**

The Study PIs will be responsible for determining whether an SAE is expected or unexpected. An adverse event will be considered unexpected if the nature, severity, or frequency of the event is not consistent with the risk information previously described for the study procedure.

### **F2c. Severity of Event**

The following scale will be used to grade adverse events:

1. Mild: no intervention required; no impact on activities of daily living (ADL)
2. Moderate: minimal, local, or non-invasive intervention indicated; moderate impact on ADL
3. Severe: significant symptoms requiring invasive intervention; participant seeks medical attention, needs major assistance with ADL
4. Life-threatening: the event is potentially fatal

### **F3. Reporting Procedures**

#### **F3a. Regulatory Event Documentation**

All regulatory events, incidents, or problems involving risks to participants, including AEs, SAEs, and Unanticipated Problems (UP), will be documented in the REDCap electronic database that houses all study data. All regulatory events will share a common electronic form template. Two separate copies of the same form will exist, (1) one for events involving information that could unblind staff to a participant's treatment allocation, and (2) another for events without details that could unblind staff to a participant's treatment allocation. Only unblinded staff will have access to the form that outlines events with details that could unblind staff to a participant's treatment intervention. The form will be filled out for every regulatory event. A study clinician will review all events that are designated AEs or SAEs to assess severity and relationship to study procedures.

The Regulatory Event form will assess the following information for all three event types (AE, SAE, and UP):

- A brief description of the incident/problem.
- Dates corresponding to event onset, stop, and location.
- Whether or not the event was unexpected or unanticipated.
- Whether or not the event placed participants or others at greater risk of harm than was previously recognized.
- The degree to which the event was related to study procedures.
- Whether or not the study procedures were discontinued due to the event.
- The steps taken to remedy the event.
- The steps taken to report the event to the appropriate entities.
- (AE/SAE only) A ranking of the severity of the event according to section F2c.
- (AE/SAE only) The specific outcome of the event.
- (SAE only) The category of the SAE.

For reporting purposes, regulatory event documentation will be aggregated into central reports using REDCap's "Reports" functionality. The "Reports" functionality allows data to be pulled from the Regulatory Event forms and summarized in one central report. The content of these reports and the frequency in which they are distributed to regulatory bodies is outlined in sections F3b. and F3c.

#### **F3b. AE Reporting**

Research staff will generate reports summarizing all AEs for each participant using the REDCap “Report” feature outlined above in section F3a. The report will contain the participant’s code number, date of AE, severity, attribution level to study, action taken, and outcome. These adverse events will be provided quarterly in this format to the DSMC, UW IRB, and NCCIH in accordance with requirements.

### **F3c. SAE/Unanticipated Problem Reporting**

- Unanticipated fatal or life-threatening SAEs at least possibly related to study procedures will be reported immediately to the NCCIH Program Officer, Chair of the DSMC, and the UW IRB.
- Breaches of confidentiality or inappropriate access to protected health information will be reported to the NCCIH Program Officer, Chair of the DSMC, and the UW IRB within 24 hours.
- Other unanticipated SAEs or serious problems at least possibly related to study procedures will be reported to the NCCIH Program Officer and DSMC Chair within 5 days, and to the UW IRB within 10 days.
- Anticipated or unrelated SAEs will be reported to the DSMC and NCCIH Program Officer as part of the annual DSM report.

Research staff will record all SAEs and unanticipated problems using the Regulatory Event form outlined above in section F3a. These serious adverse events/problems will be summarized using the REDCap “Report” format and provided quarterly in this format to the DSMC, the UW IRB, and NCCIH in accordance with requirements.

The Chair of the DSMC will be contacted when an SAE/unanticipated problem is discovered to receive consultation on the matter. The Chair of the DSMC will use her discretion to determine whether the other DSMC members should also provide additional consultation.

## **F4. Data Quality and Safety Review Plan and Monitoring**

### **F4a. Description of Plan for Data Quality and Management**

Data collected by research staff will be entered directly into a database created in REDCap, a secure HIPAA-compliant web-based system. Web forms will be created to enhance functionality and proper data entry. The REDCap system also allows researchers to create an audit trail, as well as capture an e-signature from research staff attesting to the validity of the data entered (in instances where an e-signature is specified).

All group treatment sessions will be audio recorded to ensure compliance to treatment procedures. These recordings may also be used for training purposes. A portion of treatment sessions will be randomly selected to be reviewed by study researchers to ascertain fidelity to protocol. Study clinicians will receive feedback as needed if they diverge from protocol.

In addition, research study staff will review the study data in detail on a quarterly basis to detect any systematic issues with data collection and protocol compliance. Data types that will

be reviewed include participant accrual, status of enrolled participants, adherence data regarding study assessments and intervention, any protocol deviation or violation that warrants a note-to-file, and AEs, SAEs, and unanticipated problems.

Regarding protocol deviations, only participant study visits completed outside of the protocol-defined windows would be considered protocol deviations; non-completion of study components by participants would not result in protocol deviations. This was approved by the NCCIH PO on 5/25/2018.

#### **F4b. Frequency of Data Review**

The frequency of data review for this study differs according to the type of data and can be summarized in the following table:

Data type	Frequency of review	Reviewer
Participant accrual	Quarterly	Co-PIs, Chair of DSMC
Status of all enrolled participants	Quarterly	Co-PIs, Chair of DSMC
Participant adherence to study procedures	Quarterly	Co-PIs, Chair of DSMC
AEs	Quarterly	Co-PIs, Chair of DSMC
SAEs	Per occurrence	Co-PIs, Chair of DSMC, NCCIH, UW IRB
Unanticipated Serious Problems	Per occurrence	Co-PIs, Chair of DSMC, NCCIH, UW IRB

#### **F4c. Participant Accrual and Compliance**

Review of the rate of participant accrual and compliance with inclusion/exclusion criteria will occur monthly during the first six months of recruitment and then every three months to ensure that a sufficient number of participants are being enrolled to allow for an adequate test of the primary study hypotheses and that they meet eligibility criteria.

#### **F4d. Measurement and Reporting of Participant Adherence to Treatment Protocol**

Data on participant adherence to the study protocol will be collected monthly by research staff and reviewed quarterly by the PI and the Chair of the DSMC. Adherence of participants to both assessment completion and treatment will be evaluated by running queries to discern adherence rates. If adherence falls below the rate of 80% for EMA assessments or 85% for non-EMA pre- and post-treatment assessments, which might put at risk the ability to test the study's primary hypotheses, the Chair of the DSMC will suggest a conference call for study investigators to discuss methods for improving adherence.

#### **F4e. Stopping Rules**

This study will be stopped prior to its completion if: (1) one of the interventions is associated with adverse effects that call into question the safety of the intervention; (2) any new information becomes available during the trial that necessitates stopping the trial; or (3) other situations occur that might warrant stopping the trial.

#### **F4g. Safety Review Plan**

Study researchers, including staff members and study clinicians who conduct the telephone assessments and facilitate the treatment groups, will collect safety information on an ongoing basis. By systematically monitoring for events, we will ensure that problems are detected immediately and addressed as indicated.

##### **Treatment**

Study clinicians will collect unsolicited information reported by participants during treatment sessions including, but not limited to, physical or psychological decline, or unexpected reactions to the treatment intervention.

Any AEs collected during treatment sessions will be recorded on the participant's REDCap Regulatory Events form created and completed during participation.

##### **General**

Research staff and study clinicians will collect unsolicited information reported by participants during study participation including suicidal thoughts or suicidal ideation (SI), increased alcohol/drug use, intentions to harm someone else, or psychological decline.

Any AEs collected during the course of the study will be recorded on the participant's REDCap Regulatory Events form created and completed during participation.

All information leading to an adverse event (AE), serious adverse event (SAE), or unanticipated problem (UP) will be reported per UW protocol/requirement, i.e., to UW IRB using

the approved UW IRB forms. All documentation collected, submitted, and approved will be stored in a regulatory e-binder located within a limited access folder on the study server. We do not plan to monitor charts for AEs.

Safety information collection will begin as soon as study recruitment begins. Safety information collection will end once the participant completes the final assessment, i.e., approximately six months following completion of the intervention.

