The assessment period described above will be completed prior to initiating treatment, post-treatment (after session #8), and 3 and 6 months following the end of treatment for a total of four times. These assessment periods that occur following the start of treatment will also include questions about amount of time spent practicing skills learned in treatment, treatment satisfaction and treatment modality, the importance of various treatment outcomes, and overall improvement since the participant began the treatment program. The assessments done at 3 and 6 months following the end of treatment may be completed online by the participant via REDCap instead of verbally over the telephone with research staff. Regardless of modality, the items on both the online and verbally administrated versions of the extended assessments will be the same.

The participant will also be asked additional questions at post-treatment about their experiences in the group, as well as any feedback about the treatment program. Effective 2020, there will also be a question on COVID-19's impact during treatment. These questions will be collected by an unblinded staff member and should take approximately 15-30 minutes to complete. We will audio record and code up to 100 of these interviews until we reach saturation of themes. The audio recordings will not be labeled with any identifying information. The only identifying information that will be contained within the recordings will be participants' voices and if the staff member states a participant's name during the interview.

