Second, clinicians will employ several protective measures when administering the treatment interventions. As it relates to the activation skills intervention, at the first treatment session clinicians will get to know the personal physical capabilities of each participant, allowing any future physical activity recommendations to be tailored to the individual. Further, before participants complete any assigned physical activities, the clinician will review the activity with the participant to ensure that it is reasonable and safe. Lastly, the clinician will routinely assess during the treatment phase whether participants are experiencing any adverse effects related to the activity skills intervention, and will (in conjunction with the study medical doctor, if needed) advise the participant whether they should stop or modify their activity, or recommend they seek guidance from their primary health care provider (if the event is significant but non-imminent) or urgent/emergency care (if the event is life-threatening or an urgent, acute medical issue). As it relates to the cognitive therapy and mindfulness meditation interventions, during each treatment session clinicians will routinely assess whether participants are experiencing any adverse effects related to the treatment interventions, and will (in conjunction with PI supervision, if needed) advise the participant whether they should stop or modify participation in mindfulness meditation or cognitive therapy treatment activities.

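### Active adverse-event assessment is described only for the treatment phase, where F4g contradicts it; after Session 8 no listed measure asks about adverse events

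*Protocol*

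**What the plan says.** Section F4g opens with a strong standard: "By systematically monitoring for events, we will ensure that problems are detected immediately and addressed as indicated". The rules beneath it are passive. For treatment, "Study clinicians will collect unsolicited information reported by participants during treatment sessions". For the study in general, "Research staff and study clinicians will collect unsolicited information reported by participants during study participation including suicidal thoughts or suicidal ideation (SI". The same section states "We do not plan to monitor charts for AEs" and sets the end of the safety period: "Safety information collection will end once the participant completes the final assessment, i.e., approximately six months following completion of the intervention".

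Section E4b describes something different for the treatment phase. In cognitive therapy (CT) and mindfulness meditation (MM), "during each treatment session clinicians will routinely assess whether participants are experiencing any adverse effects related to the treatment interventions". For activation skills (AS), E4b likewise has the clinician check routinely for adverse effects, over the treatment phase and without tying this to sessions.

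On follow-up, D6g says: "The assessments done at 3 and 6 months following the end of treatment may be completed online by the participant via REDCap". It adds that the items are identical in both modes. D6g also confines the weekly calls to medication use, pain intensity, catastrophizing, non-judgment, depression and anxiety. The Appendix marks AEs in all nine columns of the evaluation timeline, including the 3- and 6-month follow-ups, but names no question or form.

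**The concern.** The stated standard and the described method do not match. F1a asks staff to document an occurrence that is new for the participant and led to self-treatment or professional treatment. Staff seldom learn of such an event unless they ask. F1c makes an inpatient stay a serious adverse event (SAE), F4b has SAEs reviewed as they occur, and F3c sets short reporting times for some of them. None of this can operate on an event that staff do not know about.

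The counts are also used. The Annual Report must judge whether AE rates agree with pre-study assumptions, and the first stopping criterion in F4e depends on adverse effects linked to an intervention. Counts that mix active questioning during treatment with volunteered reports before and after it are hard to interpret. A low post-treatment count could reflect few events or few questions.

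**Working it through.** The plan gives no figure for AE ascertainment, so the main check sets the sections side by side.

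| Period | Scheduled staff contact | AE question described | Appendix AE row |
|---|---|---|---|
| Before Session 1 | Calls for screening, baseline and pre-treatment data; two weekly calls | None listed | Marked |
| Treatment | Sessions; weekly calls | Yes in E4b (all three arms); F4g says unsolicited | Marked |
| Four weeks after Session 8 | Four weekly calls | None; six other domains only | Marked |
| Post-treatment assessment (up to 2 months) | Telephone assessment; open-ended interview on group experience | None listed | Marked |
| 3 months | Online or telephone | None listed | Marked |
| 6 months | Online or telephone | None listed | Marked |

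Tables 1, 3 and 4 were read for any AE, injury or hospitalisation item and list none. The nearest is a single count of visits to a health care professional in the last month. It does not identify an event, and it does not cover the interval between assessments.

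The one quantity to compute is the post-treatment time without scheduled live contact if both follow-ups are online.

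Inputs:
- Nominal follow-up: 6 months = 26 weeks (F4g).
- Earliest last live contact: end of the four weekly calls, 4 weeks after treatment (Table 2).
- Latest last live contact: post-treatment assessment at the limit of its window, 2 months (Table 1) = 2 × 52/12 = 8.7 weeks. The interview is assumed to fall within the same window, since no separate one is given.

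Formula: gap = 26 − week of last live contact.
- Longest: 26 − 4 = 22 weeks; 22/26 = 85%.
- Shortest: 26 − 8.7 = 17.3 weeks; 17.3/26 = 67%.

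If both follow-ups are by telephone, two live contacts are added, still with no listed AE question. The 6-month window runs from 5 to 8 months, so an individual's gap may be somewhat shorter or longer.

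The revision history offers a possible reason for the E4b–F4g conflict. Section F was last aligned with the safety monitoring plan in version 2.2 (June 1, 2021). More active monitoring was added to E4b afterwards, in versions 2.21 and 2.3. F4g may simply not have been updated; this is an inference.

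**The case against.** Several stronger readings are tempting, and the documents do not support them.

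- *AEs are collected only if volunteered throughout.* E4b requires active assessment in all three arms during treatment, and for AS it is not limited to those who attend a session.
- *People who drop out are never asked anything.* D6n has reasons for attrition assessed, D6l allows contact after a missed session, D6m requires a withdrawal form, and D6p excludes from the interview only those who attended no session. These could reveal harm, although none is a repeated AE question.
- *A later event cannot be reported.* Participants receive staff contact details (D6c), E4a offers discussion of adverse experiences with a Co-PI, and volunteered reports are logged.
- *The forms contain no AE item.* The forms are not in the documents. Tables 3 and 4 list outcome and mechanism measures, while AEs go on a separate Regulatory Event form (F3a). A question could exist that the tables omit. What can be said is that none is listed and that F4g describes the method as unsolicited.

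Three further points have weight. Depression, anxiety, PTSD, medication use and global change are measured after treatment, so some deterioration would appear in the data, but no rule is stated for turning a score into an AE report. The gap of 17 to 22 weeks is a worst case that assumes both follow-ups are online, and it leaves out reminders and calls about unreturned devices. The SAP plans no AE analysis, so the consequence lies in safety oversight and in how AE counts are described, not in the efficacy results.

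What remains is that none of these supplies a scheduled AE question after treatment.

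**Conclusion.** The point holds in a limited form. E4b and F4g conflict for the treatment phase. Outside that phase, and most clearly after Session 8, the documents describe no solicited AE collection, although F4g promises systematic monitoring, runs safety collection to about six months, and the Appendix schedules AEs throughout. With both follow-ups online, about 17 to 22 of 26 weeks (67% to 85%) have no scheduled live contact.

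A reader might infer that safety follow-up stops at Session 8. It does not: calls continue for at least four weeks and volunteered events are recorded. The defect is probable under-ascertainment, which cannot be sized because the documents give no expected event rate. The conclusion rests on the measure lists being complete and on F4g describing actual practice.

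**What to change.** 1. Reconcile E4b and F4g so that one description of AE collection applies during treatment.
2. Replace the unsolicited rule in F4g with a short scripted, arm-neutral question: any new or worse health problem, injury, emergency department visit or hospital stay since last contact. Ask it in the existing weekly calls and in the post-treatment, 3- and 6-month assessments, including the REDCap web form with an alert to staff, regardless of attendance.
3. Have blinded callers record only neutral facts and pass any detail that could reveal the arm to unblinded staff, who complete the restricted form described in F3a.
4. Add the item to Table 4 so that it agrees with the Appendix.

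The cost is one to three items, about a minute per contact, an IRB amendment and more minor AEs to log. Rates would not be comparable with earlier cohorts, so AEs should be reported by collection method. The item would not reach people who complete no further contact; D5 expects 20% × 90 = 18 to be lost to follow-up.

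The SAP is dated July 2024 and written in the past tense, so collection may have closed. In that case, state the collection method for each period in the report and do not infer safety from low post-treatment AE counts.
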